8.2 Discontinuation of Treatment and Premature Withdrawal from Study

Subjects may be discontinued before their completion of the study due to:

- Adverse events;
- Unblinding when medically necessary;
- Protocol violations;
- Administrative reasons (e.g., inability to continue, lost to follow up);
- Termination of study by sponsor;
- Subject choice (e.g. Withdrawal of consent); and
- Other.

Note: In addition, any subject may be discontinued for any sound medical reason at the discretion of the Investigator.

Notification of a subject discontinuation and the reason for discontinuation will be made to the Sponsor and will be clearly documented on the eCRF.

Subjects who discontinue treatment should switch to proper maintenance treatment at the discretion of the Investigator. For subjects who discontinue treatment and do not finish at least one post-treatment data collection, a telephone follow-up should be made at least 7 days after the last dose of study drug.

Discontinued subjects will not be replaced.

8.3 Unscheduled Visits and End of Treatment/Study Exit Visit

Repeat assessments, if needed, will be captured in unscheduled visits.

End of treatment/study exit visits will be captured as unscheduled visits. At least the following procedures will be completed at these visits:

- Record AEs and SAEs (if any);

- Review concomitant medications;
- Urine samples will be collected from women of childbearing potential for pregnancy tests;
- All the study drugs/subject diaries will be collected;
- Subjects will resume pre-study treatment or receive appropriate medication treatment;
- Subjects will be told to report all the SAEs that occur within 7 days after the last dose of study drug;
- Collect the reasons for discontinuation of study. These visits may be made to ensure safety of subjects. All the procedures performed at unscheduled visits must be recorded in the source documents and the eCRF page for unscheduled visits. For any procedure indicated in the eCRF, "unperformed" should be indicated if they have not been performed;
- Assessment that may be performed at unscheduled visits:
 1. Slit-lamp biomicroscopy;
 2. Visual acuity;
 3. Intraocular pressure;
 4. Urine pregnancy test;
 5. Fundus color photography or mydriasis fundus examination;
 6. Any other assessment needed in the judgement of the Investigator.

8.4 End of Study

All subjects will be followed up by telephone call 7 days after last dose of study drug. The following procedures will be completed:

- Review ongoing AEs and SAEs (if any);
- Collection of new SAEs (if any);
- Review of concomitant medications.

Note: For the subjects who withdraw the informed consent, a telephone follow-up will be made at least 7 days after last dose of study drug.

8.5 Termination of Study

According to the contract signed with Harbour BioMed, investigators may choose to discontinue the study for any reason on a fully-informed basis.

Harbour BioMed reserves the right to terminate the study at any time due to clinical or administrative reasons. If Harbour BioMed decides to terminate the study, the termination process must be implemented by investigators within a time frame that is favorable to subjects' health conditions.

8.6 Completion of Study

Investigators will record the reasons for study completion or early withdrawal on the eCRF. The events will be classified as follows on the eCRF:

- Subjects' decision (record the reasons);
- For subjects' best benefit in the judgement of the Investigator;
- Adverse events;
- Administrative reasons (e.g. premature termination of the study);
- Lost to follow-up;
- Lack of efficacy;
- Major protocol deviations;
- Death;
- Study completion;
- Specific criteria specified in protocol (see Section 5).

9 STATISTICAL METHODS

9.1 Analysis Populations

The analysis populations in this study are defined as follows:

- **Full Analysis Set (FAS)** includes all the randomized subjects who have received at least one dose of study drug according to the principle of intention-to-treat (ITT). Subjects will be analyzed as randomized.
- **Per Protocol Set (PPS)** is a subset of the FAS population including all the subjects who do not have major protocol deviations and who complete the study. Subjects in the PP population will be analyzed as treated. Protocol deviations will be assessed before database lock and unblinding. For the subjects who have major protocol deviations (protocol violations), all their data should be eliminated from the PPS data, or the data of specific time points and/or subsequent time points should be eliminated.
- **Safety Set (SS)** includes all randomized subjects who have received at least one dose of the investigational product. The SS will be analyzed for all safety assessments. Subjects in the SS will be analyzed as treated.

In this study, the baseline data analysis will be based on the FAS. The efficacy analysis will be based on both FAS and PPS. The PPS will be used for main analysis. For the FAS, the missing data after dropout will be imputed using the Last Observation Carried Forward (LOCF) method. The observed and imputed data will be used for the analysis of FAS to assess the robustness of study results. The SS will be used for analysis of laboratory examination data, adverse events, and adverse reactions.

9.2 Determination of Sample Size

This study is expected to enroll 50 subjects in each treatment group so a total of 100 subjects will be randomized. Assuming a 20% drop out rate, 40 subjects per group are expected to complete the study.

According to the results from the US Phase II study, assuming the standard deviation is 0.7 unit for the change from baseline in the pre- to post-CAE[®] inferior corneal fluorescein staining (ICSS) score and the mean of the change from baseline in the pre- to post-CAE ICSS score is about 0.65, the efficacy results will be very promising if the difference in the mean of ICSS change for the placebo and treatment groups are greater than 0.3. If the difference < 0.1, the efficacy may not be promising.

If 40 subjects in each group will complete the study, the probability for observing the efficacy < 0.1 in this study will be about 74% if the study drug is not effective in the treatment group. If the difference in the efficacy between the treatment and placebo groups is >0.4, the probability for observing the efficacy > 0.3 in this study will be at least 75%. Other possibilities are summarized in the table below.

ICSS Actual Mean Difference	Ideal Region Mean difference ≥ 0.3	Consideration Region Mean Difference [0.1, 0.3)	Unsatisfactory Region Mean difference < 0.1
0.0	3.0%	23.3%	73.8%
0.1	9.9%	40.1%	50.0%
0.2	26.2%	48.6%	25.2%
0.3	50.0%	40.2%	9.8%
0.4	74.8%	22.7%	2.6%

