9.5 Efficacy and Safety Analysis

9.5.1 Efficacy Analysis

9.5.1.1 Primary Efficacy Analyses

For primary efficacy endpoints, the pre- to post-CAE ICSS change will be calculated as post-CAE ICSS score-pre-CAE ICSS score. The change from baseline will be calculated as visit (post-CAE-pre-CAE)-baseline (post-CAE-pre-CAE) such that a positive difference indicates the change at study visit is larger than that at baseline. In addition, treatment comparisons between treatment and placebo groups will be calculated as treatment – placebo, such that a negative result indicates a better score for the treatment group (i.e., the treatment group have a smaller increase in dry eye signs or symptoms than the placebo group).

ANCOVA models will be used to compare the change from baseline in the pre- to post-CAE[®] inferior corneal fluorescein staining at Day 57 (Visit 6) (measured by the Ora Calibra[®] scale), between 0.25% HBM9036 Ophthalmic Solution and Placebo. The ANCOVA models will include the change in pre- to post-CAE ICSS at baseline as a covariate. The primary analysis will use LOCF imputation to have a full accounting of the FAS at the Day 57 visit, as described in Section 9.7.

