1.4 Sample Size Justification

This study plans to enroll 50 subjects in each treatment group so a total of 100 subjects will be randomized. Assuming a 20% drop out rate, 40 subjects per group are expected to complete the study.

The treatment effect is of little clinical relevance if the difference between HBM9036 and placebo in the primary endpoint is greater than -0.1. In contrast, if the difference is -0.3 or less, it is considered of clinical significance and a Go decision to phase 3 will be likely.

If the difference is between -0.3 and -0.1, a decision will be made based on other data, e.g., efficacy in secondary endpoints and safety data.

The sample size is determined based on the probability of making a correct decision given the true effect size (i.e., efficacy scenario). Assuming the standard deviation is 0.7 unit, Table 1 below presents the summary of probabilities for observing the efficacy.

Table 1. Probability of making a Go, Pending, or No-Go decision, given various true effect size in $\Delta\Delta\text{ICSS}$.

True $\Delta\Delta\text{ICSS}$	Observed $\Delta\Delta\text{ICSS} \leq -0.3$ (Go Decision)	Observed $\Delta\Delta\text{ICSS}$ between -0.3 and -0.1 (Pending Decision)	Observed $\Delta\Delta\text{ICSS} > -0.1$ (No-Go Decision)
0.0	3.0%	23.3%	73.8%
0.1	9.9%	40.1%	50.0%
0.2	26.2%	48.6%	25.2%
0.3	50.0%	40.2%	9.8%
0.4	74.8%	22.7%	2.6%

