6.2.2 Analysis Methods

An ANCOVA model will be used to compare $\Delta\Delta$ ICSS at Day 57 (Visit 6) (measured by the Ora Calibra[®] scale), between HBM9036 and placebo. The ANCOVA model will include treatment and baseline Δ ICSS as the only 2 covariates. The between-group differences in $\Delta\Delta$ ICSS, two-sided 95% confidence intervals (CIs), and p-value will be reported.

Two-sample t-test will be conducted as a sensitivity analysis.

The primary analysis will be performed on the PP populations. After obtaining data sets and calculating changes from baseline, the following SAS code will be used to run the ANCOVA model on data sets:

```
PROC MIXED DATA = OUTDATA;  
  CLASS TREATMENT;  
  MODEL CHANGE_INFERIOR = BASELINE TREATMENT / SOLUTION COVB;  
  LSMEANS TREATMENT / CL PDIFF;  
  ODS OUTPUT LSMEANS = OUTLS DIFFS = OUTDIFFS;  
RUN;
```

where

- *TREATMENT* is the name of the treatment group variable
- *BASELINE* is the baseline post-CAE[®] – pre-CAE[®] inferior corneal staining score in the study eye
- *CHANGE_INFERIOR* is the post-CAE[®] – pre-CAE[®] inferior corneal staining score in the study eye at Visit 6 (Day 57 ± 3) – *BASELINE*

Sensitivity analyses will be performed:

- on the FAS population using the last observation carried forward (LOCF) - imputation method for missing values will be used which means the last value from the previous visits will be carried forward, matching pre-CAE[®] or post-CAE[®] time points and a pre-CAE[®] time point will never be imputed for a post-CAE[®] value, and vice versa to have a full accounting of the FAS at the Day 57
- on the FAS using MMRM methodology

An example of the SAS code implementation of the ANCOVA model for the FAS population using LOCF is as follows:

```
PROC MIXED;  
    CLASS TREATMENT;  
    MODEL CHANGE_INFERIOR = BASELINE TREATMENT / SOLUTION COVB;  
    LSMEANS TREATMENT / CL PDIFF;  
RUN;
```

For LOCF, baseline value will be used for post baseline if both visit 5 and visit 6 are missing.

An example of the SAS code implementation of the ANCOVA model for the MMRM is as follows:

```
PROC MIXED;  
    CLASS TREATMENT PTNO VISIT;  
    MODEL CHANGE_INFERIOR = BASELINE TREATMENT VISIT VISIT*BAELINE  
    VISIT*TREATMENT/ DDFM=KR SOLUTION CHISQ;  
    REPEATED VISIT/SUBJECT=PTNO TYPE=UN R RCORR;  
    LSMEANS TREATMENT*VISIT / PDIFF=ALL OM CL ALPHA=0.05 SLICE=VISIT;  
RUN;
```

where

- *PTNO* is Patient number (ID)
- *VISIT* is visit timepoint (5, 6)

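### The Go/Pending/No-Go probabilities describe 40 observed completers per arm, so they fit the PPS analysis but not the FAS/LOCF analysis that Protocol 9.5.1.1 and 9.7 call primary

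*Protocol*

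**What the plan says.** Both documents plan 50 per arm and treat dropout as a loss of numbers. In SAP 1.4: "Assuming a 20% drop out rate, 40 subjects per group are expected to complete the study". Protocol 9.2 sets the spread by "assuming the standard deviation is 0.7 unit for the change from baseline" and builds its table on completers ("If 40 subjects in each group will complete the study, the probability for observing the efficacy"). SAP 1.4 repeats the same probabilities and attaches decisions to them: "if the difference is -0.3 or less, it is considered of clinical significance and a Go decision to phase 3 will be likely". A difference above -0.1 is No-Go, and the band between is Pending.

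The documents do not agree on which analysis is primary:

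- Protocol 9.1 makes the PPS the main analysis, requires PPS subjects to have completed, and gives the LOCF-imputed FAS a robustness role.
- Protocol 9.5.1.1 says "The primary analysis will use LOCF imputation to have a full accounting of the FAS at the Day 57 visit", and Protocol 9.7 repeats LOCF for the primary efficacy analyses.
- SAP 6.2.2 makes the PP set primary and lists FAS/LOCF and an FAS MMRM as sensitivity analyses.

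For the LOCF analysis, SAP 6.2.2 adds: "For LOCF, baseline value will be used for post baseline if both visit 5 and visit 6 are missing". By Protocol 4.1 and Table 1, the only post-baseline CAE exposures are at Visits 5 and 6.

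**The concern.** The sample size has no other justification than these probabilities, and the phase 3 decision is read from the same two cut-offs. Under LOCF on the FAS, the expected dropouts stay in the comparison. A subject who leaves before Visit 5 has no on-treatment pre- to post-CAE change, so under the SAP rule that subject scores zero in either arm. This pulls the expected treatment difference toward zero while the cut-offs stay where they are.

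A team following Protocol 9.5.1.1 would then quote probabilities that belong to a different estimate. A team following the SAP could hold the FAS/LOCF sensitivity result against -0.3 and mistake dilution for a lack of robustness.

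**Working it through.** Differences are written as benefit, so the SAP's -0.3 and -0.1 become 0.3 and 0.1.

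**Inputs from the documents.** 50 randomized and 40 completers per arm, 20% dropout, SD 0.7 (Protocol 9.2); cut-offs 0.3 and 0.1 (SAP 1.4); CAE after baseline only at Visits 5 and 6 (Protocol 4.1, Table 1); baseline carried forward if both are missing (SAP 6.2.2).

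**Assumptions.** Equal dropout in the arms; placebo mean change -0.65 (Protocol 9.2 gives about 0.65 with neither sign nor arm); subjects leaving after Visit 5 carry the full effect; a share e of dropouts leaves before Visit 5.

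**Step 1: reproduce the printed table.** SE = 0.7 × √(2/40) = 0.1565. Go = Φ((d − 0.3)/SE); No-Go = Φ((0.1 − d)/SE).

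| True difference d | Go printed | Go recomputed | No-Go printed | No-Go recomputed |
|---|---|---|---|---|
| 0.0 | 3.0% | 2.8% | 73.8% | 73.9% |
| 0.1 | 9.9% | 10.1% | 50.0% | 50.0% |
| 0.2 | 26.2% | 26.1% | 25.2% | 26.1% |
| 0.3 | 50.0% | 50.0% | 9.8% | 10.1% |
| 0.4 | 74.8% | 73.9% | 2.6% | 2.8% |

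All cells agree within about 1 point. With 50 per arm (SE 0.14), 7 of the 15 cells miss by more than 2 points. The table is therefore for 40 per arm with an undiluted effect.

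**Step 2: FAS/LOCF with 50 per arm.** Let q = 0.20e be the share scored zero. The expected difference is d(1 − q). The variance in each arm is 0.49(1 − q) + q(1 − q)μ², with μ = -0.65 on placebo and -0.65 − d on active. SE = √((sum of the two variances)/50).

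Example, d = 0.4 and e = 0.5: q = 0.10 and the difference is 0.36. Placebo variance = 0.441 + 0.09 × 0.4225 = 0.479; active variance = 0.441 + 0.09 × 1.1025 = 0.540. SE = √(1.019/50) = 0.1428. Go = Φ(0.06/0.1428) = 66.3%.

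| Dropouts leaving before Visit 5 | Expected difference at 0.4 | Go at 0.4 | No-Go at 0.4 | Expected difference at 0.3 | Go at 0.3 | No-Go at 0.3 |
|---|---|---|---|---|---|---|
| none | 0.40 | 76.2% | 1.6% | 0.300 | 50.0% | 7.7% |
| a quarter | 0.38 | 71.4% | 2.4% | 0.285 | 45.8% | 9.5% |
| half | 0.36 | 66.3% | 3.4% | 0.270 | 41.6% | 11.5% |
| all | 0.32 | 55.5% | 6.2% | 0.240 | 33.5% | 16.1% |
| *printed, 40 completers* | 0.40 | 74.8% | 2.6% | 0.300 | 50.0% | 9.8% |

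**Step 3: sensitivity.** If all dropouts leave early, moving the placebo mean from 0 to -1.0 moves Go from 56.2% to 55.0% at 0.4 and from 31.7% to 35.0% at 0.3. A simulation of the ANCOVA with baseline-to-change correlation from 0 to -0.6 gives 68–71% (half) and 55–57% (all) at 0.4.

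Equal dropout matters more. With 15% dropout on placebo and 25% on active, all early, Go at 0.4 is 50% if the placebo mean is 0 and 33% if it is -0.65. It is 69% if the placebo mean is +0.65.

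**Step 4: the PPS reading.** If deviations cut the PPS to 36 per arm, SE = 0.7 × √(2/36) = 0.165 and Go at 0.4 is 72.8%, 2 points below print.

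**The case against.** The strongest reply is that the plan is coherent on its own main reading. Protocol 9.1 names a completer-based PPS as the main analysis, SAP 6.2.2 makes PP primary, and Protocol 9.2 conditions its figures openly on 40 completers. The table contains no arithmetic error. The zero-change rule is written only in the SAP, where FAS/LOCF is a sensitivity analysis. Protocol 9.7 says that earlier values are carried forward with pre- and post-CAE matched, and is silent on someone with no later CAE. No passage applies the cut-offs to a sensitivity analysis. The SAP's MMRM on the FAS already offers an estimate without inserted zeros.

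All of this stands, and it limits the point. It does not remove it: Protocol 9.5.1.1 and 9.7 are current text, and SAP 1.4 ties the cut-offs to the primary endpoint without naming an analysis set.

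Three stronger readings are tempting, and the documents do not support them:

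- *The table is miscalculated.* It reproduces.
- *The real Go chance is 56%.* That needs every dropout to leave before Visit 5. The documents give neither dropout timing nor the Visit 5 effect, and if nobody leaves early the figure is 76%, slightly above print.
- *The FAS result would miss the Go line even for a drug that works.* At a true 0.4 the expected LOCF difference is 0.32 to 0.40 and Go stays above 50% in every equal-dropout case shown. With half leaving early, the expected value falls below 0.3 only for true differences under 0.3/0.9 = 0.33.

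**Conclusion.** The concern holds in a limited form. The decision probabilities are correct for observed completers and so describe only one of the two analyses that the protocol presents as its principal one. For FAS/LOCF, the loss in Go chance at 0.4 is about 8 points against print if half of the dropouts leave before Visit 5 and about 19 if all do. There is a gain of about 1 point if none do.

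The range rests on equal 20% dropout, SD 0.7, the SAP's zero-change rule and a full Visit 5 effect. It is not a bound. Unequal dropout can move the figure either way, and a smaller effect at Visit 5 would lower it. Unequal dropout is plausible: Protocol 1.4.2 reports eight withdrawals for allergic conjunctivitis in the US study, all on active drug. The firmest part is the conflict over the primary analysis, which depends on none of these assumptions.

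**What to change.** 1. Reconcile Protocol 9.1, 9.5.1.1 and 9.7 with SAP 6.2.2 on one primary analysis.
2. In Protocol 9.2 and SAP 1.4, label the table as *observed completers, n = 40 per arm, no imputation*.
3. State that the -0.3 and -0.1 cut-offs apply to that estimate and are not to be read unchanged against the LOCF estimate.
4. For an FAS reading against the cut-offs, use the Visit 6 contrast of the MMRM already in SAP 6.2.2. It inserts no zero changes but relies on missing at random.
5. If FAS/LOCF is kept as primary, restate the probabilities for it, with the dropout-timing assumption shown.

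The cost is wording and, in the last case, one recomputed table. The stated Go chance for FAS/LOCF may look less favourable. No extra subjects, visits or data are needed.

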9.3 Blinding and Randomization

Random numbers will be generated at a ratio of 1:1 (treatment group to control group) using the randomized block method by independent biostatisticians responsible for the data management and statistical analysis of this study. The selected block size and random seeds will be kept confidential. Statisticians unrelated to this study will label study drugs with the random number. Each study site will use the assigned code according to the sequence of enrollment.

This study will use the centralized randomization method and each study site will enroll subjects competitively. For each eligible subject, the study staff at study sites will log into the IWRS system, complete screening information, and obtain the random number and corresponding drug number. Investigators will dispense study drugs according to the random number and drug number.

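### The 'at least 75%' chance of a Go result in Protocol 9.2 is slightly too high: its own table gives 74.8% and its stated inputs give 73.9% at a true difference of 0.4

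*Protocol*

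**What the plan says.** Protocol section 9.2 plans the trial around how likely the observed difference is to fall in each of three regions. The region that supports going on is headed "Ideal Region Mean difference ≥ 0.3". The lowest region is an observed difference below 0.1, and the middle one lies between the two limits.

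The inputs are in the same section:

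- Standard deviation: "assuming the standard deviation is 0.7 unit for the change from baseline" in the pre- to post-CAE staining score.
- Size used in the calculation: "If 40 subjects in each group will complete the study". This comes from 50 randomized per group less 20% dropout ("Assuming a 20% drop out rate, 40 subjects per group are expected to complete the study").

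The text then gives two headline probabilities. With an ineffective drug, the chance of observing less than 0.1 is put at about 74%. With a true difference above 0.4, "the probability for observing the efficacy > 0.3 in this study will be at least 75" per cent. The table below prints 73.8% for the first (true difference 0.0) and 74.8% for the second (true difference 0.4).

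SAP section 1.4 keeps the table, with the regions renamed Go, Pending and No-Go ("Assuming the standard deviation is 0.7 unit, Table 1 below presents the summary of probabilities for observing the efficacy"). It does not repeat the sentence with the 75% figure. It does say that the sample size was set by the probability of a correct decision.

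**The concern.** The sentence states a lower bound that the table beneath it does not meet: 74.8% is less than 75%. The two headline figures should also be the same number. An observed difference that falls short of a true 0.4 by no more than 0.1 is the mirror image of one that exceeds a true 0.0 by less than 0.1. One is nevertheless reported as about 74% and the other as at least 75%.

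These probabilities are the plan's whole justification for its size and describe how the Phase 3 decision rule behaves. The headline figure errs in the favourable direction, and a reader can check it against the line below it.

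**Working it through.** **Model.** Differences are read as benefit of active over placebo, as in the Protocol table. Allocation is 1:1, the SD is common to both groups, and the observed mean difference is taken as normal. The two-sided 0.05 level plays no part, because the rule is a threshold on the point estimate.

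- SE = 0.7 × √(2/40) = 0.1565
- P(Go) = 1 − Φ((0.3 − δ)/SE)
- P(No-Go) = Φ((0.1 − δ)/SE)
- P(Pending) = 1 − P(Go) − P(No-Go)

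**The plan's figures against the formula (Go / Pending / No-Go, %)**

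| True difference | Printed in both documents | Calculated |
|---|---|---|
| 0.0 | 3.0 / 23.3 / 73.8 | 2.8 / 23.4 / 73.9 |
| 0.1 | 9.9 / 40.1 / 50.0 | 10.1 / 39.9 / 50.0 |
| 0.2 | 26.2 / 48.6 / 25.2 | 26.1 / 47.7 / 26.1 |
| 0.3 | 50.0 / 40.2 / 9.8 | 50.0 / 39.9 / 10.1 |
| 0.4 | 74.8 / 22.7 / 2.6 | 73.9 / 23.4 / 2.8 |

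Every printed cell is within 1 point of the formula, so the method and inputs are as described. Calculated rows may miss 100 by 0.1 through rounding.

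**The headline cell.** At δ = 0.4, (0.4 − 0.3)/0.1565 = 0.639 and Φ(0.639) = 0.7385 (unrounded 0.73855), or 73.9%. That is 0.95 points below the table and 1.15 points below the text. A t distribution with 78 degrees of freedom gives 73.8%.

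**What would give 75%** (Φ⁻¹(0.75) = 0.6745)

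- True difference: 0.3 + 0.6745 × 0.1565 = 0.4056, about 0.406.
- Completers at 0.4: 2 × (0.7 × 0.6745/0.1)² = 44.6, so 45 per group.
- SD at 0.4 with 40 per group: (0.1/0.6745)/√(2/40) = 0.663.

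**Symmetry.** The thresholds 0.1 and 0.3 are equally far from 0.2, so under this model three pairs must match:

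- Go at 0.4 and No-Go at 0.0: printed 74.8 and 73.8, both 73.9.
- Go and No-Go at 0.2: printed 26.2 and 25.2, both 26.1.
- Go at 0.0 and No-Go at 0.4: printed 3.0 and 2.6, both 2.8.

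No single standard error reproduces the printed cells: 73.8% implies 0.1569 and 74.8% implies 0.1497.

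**Could half-grade scoring explain it?** The scale allows 0.5 steps, so with 40 per group the raw mean difference moves in steps of 0.5/40 = 0.0125 and can land exactly on a threshold. Rounding individual normal scores to half units raises Go at 0.4 to 74.7%. It also gives No-Go at 0.1 as 48.4% and Go at 0.3 as 51.6%. The table prints 50.0% for both, so it was not built that way.

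**The case against.** The strongest reply is that this is rounding. 74.8% rounds to 75%, just as the neighbouring sentence rounds 73.8% to about 74%. The sentence also concerns true differences above 0.4, so its bound fails only between 0.400 and about 0.406, on a scale scored in half grades. The SD is a one-decimal planning value, and moving it from 0.7 to 0.663 closes the whole gap. If the table was simulated, 1 point is ordinary error: with 2,000 runs the standard error of such a cell is √(0.738 × 0.262/2000), about 1 point. The documents do not say how the table was made, so simulation is only a possibility.

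Most of this stands, and it limits the point to a restatement. It does not make the bound true. Just above 0.4 the probability is 73.9% by formula and 74.8% by interpolation from the plan's own table, so 'about' would be defensible and 'at least' is not. Nor does it remove the mismatch between cells, which can be calculated exactly.

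A reader might go further and infer that the design fails to deliver its promised success probability, or that the shortfall is larger because the per-protocol set will hold fewer than 40 per group. The documents support neither. A gap of about 1 point is well inside the uncertainty of the SD. No expected number of per-protocol exclusions is given. The analysed number could also exceed 40: Protocol section 9.5.1.1 describes the primary analysis as LOCF on the full analysis set. With all 50 per group and the SD unchanged, SE = 0.14 and the probability is 76.2%. Adjustment for baseline in the ANCOVA could reduce the standard error further.

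**Conclusion.** The point holds as a minor correction. At a true difference of 0.4 the stated inputs give 73.9%, against 74.8% in both tables and a claimed minimum of 75% in the Protocol text. The claim is true only from about 0.406 upward. Both tables contain mismatched pairs, apart by 1.0, 1.0 and 0.4 points. The SAP shares the table but not the faulty sentence.

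This rests on the plan's own SD and completer number, a common SD and a normal observed difference. It does not show that the trial is too small. The 50 per group, the 40 expected completers and the 0.3 and 0.1 thresholds all stay as they are, and no test or significance level depends on the figure.

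**What to change.** In Protocol section 9.2, replace the lower bound of 75% with 'about 74% at a true difference of 0.4'. In that section and in SAP Table 1, replace the cells with the calculated values (Go / Pending / No-Go, %):

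- 0.0: 2.8 / 23.4 / 73.9
- 0.1: 10.1 / 39.9 / 50.0
- 0.2: 26.1 / 47.7 / 26.1
- 0.3: 50.0 / 39.9 / 10.1
- 0.4: 73.9 / 23.4 / 2.8

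State beside each table that it uses a normal approximation with SD 0.7 and 40 per group. A second set of values for another analysed number is optional. The cost is one sentence and two tables, with a headline figure about 1 point less favourable.
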